We hypothesise that earlier detection of a major anomaly could alter women's preferences for continuing a pregnancy and so will construct our model to simulate the impact on the pregnancy termination rate and the number of babies born with a major anomaly. An increased risk of miscarriage from invasive testing following a false positive early screen will also be considered. Equally important is the impact on parents. The psychological sequelae of terminating a pregnancy for a major anomaly are significant and any additional burden should be reflected (10, 11, 55, 56). Furthermore, the potential for false positive results with early screening and the associated anxiety and morbidity from additional invasive testing must also be considered. In contrast, earlier anomaly detection and intervention may avert some of the distress, and may avoid the additional pressures that parents feel to reach a decision about their pregnancy before the 24-week legal termination limit (55). Also, and should a termination be chosen, an earlier procedure may expose women to less physical harm than a later procedure. We plan to explore the likely net impact of all of these consequences upon maternal and parental utility during the pregnancy.

We foresee a need to compare variants of protocols (with different anatomical specifications / screening modalities and personnel / interventional pathways) and expect to operationalise these as alternative comparators within a decision tree model covering each of the three trimesters to birth. Within each trimester, the model will be structured for any anomaly screening results, related prevalence and sensitivity/specificity and intervention pathways, and will be populated with data on associated event

probabilities, costs, and parental and infant payoffs. Separate outcomes will be presented using the decision tree and will include births with a major anomaly, and maternal and parental utility during the pregnancy (expressed as quality adjusted life years (QALYs)). At this stage, we anticipate a paucity of data on the false positive rate (and hence specificity) of tests. The statistics will also vary by anomaly. Where data are not forthcoming we will seek expert opinion using a structured elicitation technique (e.g. SHELF) (57).

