If the hypotheses above are correct, the implications of first trimester anomaly screening will extend beyond the pregnancy. For example, there may be long term cost-savings for the NHS and social services as well as a reduction in the parental burden of caring for a child born with a major anomaly. However, the notion that these benefits are realised through an increase in the number of pregnancies being terminated is ethically challenging. Indeed, the likely preferences of society for such a program are unclear. This in turn raises questions about the use of conventional cost-utility analyses whereby results are interpreted within the context of society's valuation of a QALY (54, 58). Although our primary approach will take the form of a cost-consequence analysis, we will also calculate incremental cost-effectiveness ratios, but would emphasise that in the light of the sensitivities discussed above, that these should be interpreted with caution.

Protocol alternatives and input parameters for the model will be informed by WPs 1, 2, and 3 as well as by supplementary literature searching and expert elicitation. We will utilise the planned national survey to elicit information on pregnancy termination rates with and without first trimester anomaly screening and will interrogate the Department of Health's termination statistics. Cost data will be sourced from administrative datasets, hospital finance departments, and the published literature. Model parameters will be entered as distributions and the resulting simulated costs and outcomes of each alternative will be compared to rule out dominated and extended dominated protocols. Incremental cost-effectiveness ratios (and/or net health/monetary benefit) will be computed for the remaining protocols and a VoI analysis conducted. These analyses will be conducted for various outcomes (including the number of births with an anomaly, and maternal quality adjusted life years) so as to make clear the social value judgements that arise when outcomes for different affected parties are considered. As a secondary analysis, we will also perform these works using the long-term cost and QALY framework, if viable.

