4.2. Value of Information (VoI) analysis

Using the model's facility for probabilistic sensitivity analysis, we will calculate the expected value of perfect information (EVPI) and partial perfect information (EVPPI) and if either suggests value from future research, we will explore the expected value of sample information (EVSI), expected costs, and the expected net gain of sampling (ENGS) for various trial designs and sample sizes.

VoI analysis is complicated by the inability to calculate a single meaningful incremental cost per QALY gained from the screening intervention. We will, therefore, conduct these from the outcome perspectives of the mother, both parents, and if appropriate, from society too. The exact specification will be determined prior to analysis, but may, for example, in the case of the mother and parental perspectives, lead to the outcome being dichotomised into 'desirable' or 'undesirable', where a desirable outcome is one where a fetus is either carried to term or terminated in accordance with the wishes of the parent(s). Thus, the driver for 'undesirable' outcomes will be a function only of the false positive and negative rate of the screening test, thereby avoiding any social value judgements associated with the decision itself. The EVSI will then be interpreted as the expected gain in 'desirable' outcomes from additional information yielded from a trial. The cost and EVSI from alternative trial designs can then be compared in stepwise manner, excluding dominated and extended dominated options.

WP 5: Determining the final study design

We will draw together the findings and recommendations from the project, and, if appropriate, outline the design of plausible prospective studies. The Vol analysis will be rerun to predict the expected net gain of sampling (ENGs) of these. Where appropriate, this will include identifying the most efficient sample size for such studies, the range of sample sizes yielding a positive ENGs, and comparisons with the sample size yielded from a traditional power calculation.

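### As written, dominated protocols are ruled out before the value of information analysis, which can understate EVPI, EVPPI and EVSI but never overstate them

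*Protocol*

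**What the plan says.** All references are to the Protocol, section 6 (Research Plan), WP 4, unless stated.

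- **Comparators (4.1).** Several screening variants will enter one decision model: "We foresee a need to compare variants of protocols".
- **Probabilistic model (4.1).** "Model parameters will be entered as distributions and the resulting simulated costs and outcomes of each alternative" are then "compared to rule out dominated and extended dominated protocols".
- **Next step (4.1).** Incremental cost-effectiveness ratios, or net benefit, "will be computed for the remaining protocols and a VoI analysis conducted". The text adds: "These analyses will be conducted for various outcomes".
- **VoI (4.2).** EVPI and EVPPI are calculated with the model's probabilistic sensitivity analysis. EVSI, trial cost and ENGS are explored only if one of the two points to value in research. No set of screening protocols is named. The one exclusion of dominated options in 4.2 concerns trial designs, which is a separate step.
- **Uncertainty (4.1).** On false positives the authors write: "we anticipate a paucity of data on the false positive rate (and hence specificity) of tests".

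**The concern.** Ruling out dominated options is correct for an incremental cost-effectiveness table, because such an option is not the choice on current expected values at any threshold. VoI asks a different question: how much would be gained if better information changed the choice? A protocol that trails on its expected values may be the one that better information would favour. If it has been removed, that gain is not counted.

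The project's title asks whether a prospective study is an efficient investment, and VoI supplies the answer. EVPI and EVPPI also act as a gate: if they look too small, EVSI and ENGS are not pursued. Section 15 says that if no further research appears worthwhile, the model will be used to inform policy instead. An error that can only go one way, at the first gate, is therefore worth removing.

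**Working it through.** **The plan's own figure.** The Protocol states no EVPI, EVPPI, EVSI or VoI-based sample size, so there is nothing to reproduce. The check is algebra plus simulation. Every numerical input below is assumed.

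**Algebra.** For an option set D with net benefit NB,

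EVPI(D) = E[max over D of NB] − max over D of E[NB].

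EVPPI and EVSI have the same form, with NB in the first term replaced by its mean given the parameter of interest, or given the trial data.

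1. *Second term.* If option d has higher expected cost and lower expected effect than another option, its E[NB] is lower at every threshold ≥ 0. If d is extended dominated by a mix of A and B with weight w, then E[NB_d] ≤ w·E[NB_A] + (1 − w)·E[NB_B] ≤ max(E[NB_A], E[NB_B]). Dropping d leaves the second term unchanged.
2. *First term.* A maximum over fewer options cannot be larger. It falls strictly if d is best with positive probability.
3. Hence each VoI measure on the reduced set is at most its value on the full set.

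**Illustration 1: five options, 1,000,000 draws.** Mean costs 0, 20, 25, 60, 42; mean effects 0, 0.0020, 0.0019, 0.0045, 0.0030; threshold 20,000 per unit of effect; cost SD 5; a trial resolving half the effect variance. The third option is dominated by the second (25 v 20; 0.0019 v 0.0020). The fifth is extended dominated: its ratio against the second is 22/0.0010 = 22,000, while moving from it to the fourth costs 18/0.0015 = 12,000. Neither had the highest E[NB] at any threshold from 0 to 200,000.

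| Effect SD | Correlation | P(a removed option is best) | EVPI full → reduced | EVPPI full → reduced | EVSI full → reduced |
|---|---|---|---|---|---|
| 0.0005 | 0.5 | 0.157 | 2.30 → 1.44 (−37%) | 1.30 → 0.84 (−35%) | 0.36 → 0.26 (−29%) |
| 0.001 | 0 | 0.340 | 12.79 → 7.36 (−42%) | 12.20 → 7.03 (−42%) | 6.74 → 3.96 (−41%) |
| 0.001 | 0.5 | 0.277 | 7.64 → 4.64 (−39%) | 6.87 → 4.21 (−39%) | 3.31 → 2.04 (−38%) |
| 0.002 | 0.9 | 0.211 | 10.00 → 8.02 (−20%) | 9.29 → 7.59 (−18%) | 4.12 → 3.33 (−19%) |

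Over effect SDs 0.0002 to 0.002 and correlations 0 to 0.9, EVPI fell by 20% to 42%. EVPPI and EVSI fell wherever they were not negligible. With an option dominated in every draw, EVPI did not change (0.080 v 0.080).

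**Illustration 2: how far the size depends on the assumptions.** Baseline 0; A with effect 1.0 (SD 0.4) and cost 10 (SD 3); B with 0.8 (0.3) and 8 (2); C with 0.95 and cost 11 (3), dominated by A on means; threshold 12. Expected net benefits are 0, 2.0, 1.6 and 0.4. Loss in EVPI from dropping C (2,000,000 draws):

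| Effect SD of C | Effect loading 0.5 on a shared factor, costs independent | Loading 0.95 on shared effect and cost factors |
|---|---|---|
| 0.3 | 3.30 → 2.65 (−20%) | 1.75 → 1.68 (−4.5%) |
| 0.4 | 3.52 → 2.65 (−25%) | 1.83 → 1.68 (−8%) |
| 0.5 | 3.80 → 2.65 (−30%) | 2.01 → 1.68 (−17%) |
| 0.6 | 4.11 → 2.65 (−36%) | 2.30 → 1.68 (−27%) |

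Moving C further from the frontier (effect 0.8, SD 0.4, cost 12) gives a loss of 12% with the weaker correlation (3.02 → 2.65) and 0.5% with the stronger (1.692 → 1.684).

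**The case against.** **The restriction is inferred.** Grammatically, the phrase about the remaining protocols attaches to the computation of ratios or net benefit, and the VoI clause names no set. Section 4.2 says nothing of exclusion and leaves its exact specification until before the analysis. This stands as a caution. But the only order written down places VoI after the exclusion, and the deferred specification is introduced in connection with the outcome measure. The point concerns a stated sequence rather than missing detail.

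**Dominance on expected values is also inferred.** It is the usual convention, not the Protocol's wording. If only protocols dominated in every draw were dropped, nothing would be lost.

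**The 4.2 example uses another metric.** For the mother and parents, outcomes may be dichotomised as desirable or undesirable, so not every VoI analysis need inherit the set from 4.1. That is fair, and naming the set would settle it.

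**The size may be small.** Variants within one decision tree share inputs such as prevalence, so they may be strongly correlated. This stands: the loss can be near zero.

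**Readings that go too far.** A reader might infer that the efficient sample size is understated. Lower EVSI means ENGS is too low or unchanged at each sample size, but the optimum depends on marginal EVSI against marginal cost, and its direction is not established. A reader might also object that the protocol set could differ between outcomes. The plan deliberately runs and reports these analyses separately, so that is not shown to be an error.

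**Conclusion.** The point holds as a correction to the stated sequence. If VoI is run on the protocols left after exclusion, and dominance is judged on expected cost and effect, then EVPI, EVPPI and EVSI are understated or unchanged, never overstated. They are strictly understated if a removed protocol is best in some draws. That is plausible given the scarce specificity data that the authors expect.

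The size cannot be derived from the Protocol. In the assumed models the loss in EVPI ran from about 0.5% to about 42%, and was zero for an option dominated throughout; no single figure should be quoted as the bias in this project. The practical risk is that the EVPI/EVPPI gate closes when it should open. Whether it would depends on how close population EVPI lies to the cost of research, which the Protocol does not show.

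**What to change.** In 4.1, and again in 4.2, state that dominance and extended dominance serve only to present the cost-effectiveness frontier and the incremental ratios. State that EVPI, EVPPI, EVSI and ENGS are computed over all modelled protocols plus current practice in each outcome analysis, and that a protocol is left out only if its probability of being optimal in the probabilistic draws is negligible. Reporting that probability for each protocol would let readers check any exclusion.

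The cost is a sentence or two in each section and slightly more computing. The ratio table and the choice on current evidence do not change.

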4.2. Value of Information (VoI) analysis

Using the model's facility for probabilistic sensitivity analysis, we will calculate the expected value of perfect information (EVPI) and partial perfect information (EVPPI) and if either suggests value from future research, we will explore the expected value of sample information (EVSI), expected costs, and the expected net gain of sampling (ENGS) for various trial designs and sample sizes.

VoI analysis is complicated by the inability to calculate a single meaningful incremental cost per QALY gained from the screening intervention. We will, therefore, conduct these from the outcome perspectives of the mother, both parents, and if appropriate, from society too. The exact specification will be determined prior to analysis, but may, for example, in the case of the mother and parental perspectives, lead to the outcome being dichotomised into 'desirable' or 'undesirable', where a desirable outcome is one where a fetus is either carried to term or terminated in accordance with the wishes of the parent(s). Thus, the driver for 'undesirable' outcomes will be a function only of the false positive and negative rate of the screening test, thereby avoiding any social value judgements associated with the decision itself. The EVSI will then be interpreted as the expected gain in 'desirable' outcomes from additional information yielded from a trial. The cost and EVSI from alternative trial designs can then be compared in stepwise manner, excluding dominated and extended dominated options.

WP 5: Determining the final study design

We will draw together the findings and recommendations from the project, and, if appropriate, outline the design of plausible prospective studies. The Vol analysis will be rerun to predict the expected net gain of sampling (ENGs) of these. Where appropriate, this will include identifying the most efficient sample size for such studies, the range of sample sizes yielding a positive ENGs, and comparisons with the sample size yielded from a traditional power calculation.

If a study is deemed efficient, we will develop the relevant parameters. Possible designs include a prospective cohort screening study with ascertainment of outcomes; here we would explore whether it is acceptable to women and caregivers not to reveal those anomalies that are associated with a high false positive rate or thought to resolve spontaneously in a large number of cases, e.g. small exomphalos or megacystis of <15mm diameter (14, 59).

It would also be possible to undertake a randomised trial with women randomised to having or not having the first trimester anomaly screening test. All women in the screened arm who have a positive first-level result would then have further detailed assessment.

We will also consider the possibility of randomising at hospital level, e.g. using a cluster or stepped wedge RCT. Finally, we would also consider the potential use of an adaptive trial design. The team includes a senior statistician and leading trialists ([name], [name], [name], [name]), who have extensive experience of different methodological approaches.

Details of candidate study designs will be defined in specifically designed workshops with the PPV group. Particular aspects will be acceptability of:

- different study designs;
- reporting only major anatomical landmarks and blinded research elements for more detailed assessment;
- non-disclosure of suspected (but unconfirmed) anomalies;
- consent procedure.

The impact of declining or accepting screening for chromosomal abnormalities, including cell-free DNA screening, will be assessed in the context of anomaly screening. This is important as some anomalies (e.g. exomphalos, megacystis, holoprosencephaly) are strongly associated with trisomy 13 and 18 (60, 61). Hence, detecting such anomalies may itself increase the chances of a pregnancy being affected by such a trisomy.

WP 6: Analysis of UK-based data currently held by the National Congenital Anomalies Disease Registry

This work package is a new addition to version 9 of the protocol and was developed in response to findings from the work undertaken in WP1 and WP2. The nationwide survey of current ultrasound practice in England has shown that at present 75% of NHS Trusts routinely assess fetal anatomy in the first trimester, despite the absence of national policy. However, there is significant variation in practice seen between trusts regarding the anatomical structures evaluated in the first trimester, the anatomical image views obtained by sonographers routinely, the amount of time spent on scanning, and the training provided to sonographers.

Given that many trusts are already performing some form of first trimester anomaly scan, it is now feasible to use UK specific data (collected routinely by NCARDRS) from these ultrasound units in order to model the impact of the first trimester anomaly scan on the timing of fetal anomaly diagnoses, the timing of investigations (such as CVS/amniocentesis) and the timing of termination of pregnancy. Ultimately, this should allow us to determine whether trusts performing a routine first trimester anomaly scan are able to provide their patients with an earlier diagnosis than those trusts which do not offer this service, what system factors are associated to allow this, and whether this has any impact on patient outcomes. This data will be used in conjunction with the international literature-based data collected in WP1 to develop a more accurate and precise health economics model in WP4.

This work involves a collaboration between our group, NCARDRS and PHE. It will involve two members (AP and research fellow, JK) to obtain honorary research contracts from PHE and for the work to be formally approved by research ethics committee.

WP 7: Determining the acceptability of the early anomaly scan amongst women and their partners

This work package is a new addition to version 9 of the protocol, although a large part of this work was previously included as part of WP3. This was done partly as the original protocol had planned for in person focus groups and workshops to be conducted in order to understand parent experiences of fetal anomaly screening, to explore whether women who decline or accept screening for chromosomal abnormalities (commonly the current focus of first trimester ultrasound) would decline or accept first trimester anomaly screening and to determine the acceptability of the early anomaly scans amongst parents. Given the logistical difficulties presented by the Covid pandemic, we have introduced WP7 in an effort to allow parental opinions to inform our research and the design of the trial intervention (WP5).

WP7 will involve the distribution of a validated, prospective survey to two distinct participant cohorts in an effort to understand parental attitudes to a future first trimester anomaly scan.

Cohort A:

This will involve distribution of the survey to women who are currently pregnant and their partners. Women and their partners will be approached to participate in the study upon their arrival for routine NHS obstetric ultrasound screening at one of ten participating units across England and Wales.

Cohort B:

This will involve distribution of the survey to parents who have previously experienced a screen-positive result following ultrasound screening for fetal anomalies in pregnancy, or who have experience of a child affected by a fetal anomaly. We will aim to target those who proceeded with termination of pregnancy and those who continued with the intent of live birth. We will also aim to include parents who received a false positive screening result. Women and their partners will be approached to participate in the study one of several national charities collaborating with this project, which including Antenatal Results and Choices (ARC) and Spina Bifida, Hydrocephalus, Information, Networking, Equality (SHINE).

7. Health technologies being assessed:

The health technology being assessed is fetal ultrasound assessment in the late first trimester of pregnancy. Considerable advancements in ultrasound technology in image quality, resolution and signal processing have fuelled interest in this field. Given that the majority of fetal organ development is complete by 10 weeks of gestation, ultrasound has the potential to be a valuable tool for early fetal structural anomaly screening.

Ultrasound is already established as a test in the first trimester of pregnancy (to diagnose miscarriage, multiple pregnancy, and major chromosomal abnormalities) and in mid-gestation (principally to screen for congenital anomalies) (5, 6).

However, ultrasound is currently only used selectively for anomaly detection in the first trimester. The current project aims to assess the potential, on the basis of all existing evidence, for adding fetal anomaly detection to the first ultrasound scan for all pregnant women. The advantages of earlier diagnosis need to be balanced against lower sensitivity (in particular cardiac defects and spina bifida); false positive rates; and cost. The first can be overcome by maintaining the second scan; the second and third have been under-studied in the existing literature.

Although the focus is on ultrasound, the way this fits into the overall screening “landscape” will be assessed; thus the impact of changing rates of accepting / declining screening for chromosomal abnormalities, including cell-free DNA screening, will be evaluated.

8. Design and theoretical/conceptual framework:

The project involves multiple study designs. First, it will involve systematic literature search and meta-analysis of data from studies that assess the detection rates for fetal anomalies using ultrasound examinations in the first trimester. Second, it will involve sensitivity analyses of studies that describe the effect of factors in detection rates. Third, survey results of current practice will allow the feasibility of implementation of protocol-driven screening in the UK, and consensus will be developed to define the protocol for such screening. This will also include objective image criteria that currently do not exist: for example, in the second trimester image criteria determine which aspects of the head should be seen when circumference is

measured; this allows optimal imaging and the quality of image acquisition to be audited. Similar image criteria need to be determined for the first trimester (5). Fourth, decision analytic modelling will be employed to determine whether a program of screening and intervention, with performance as estimated on the above evidence synthesis, would be cost effective when compared with other medical expenditure in the UK. Fifth, it will involve a value of information analysis that assesses the economic case for performing a research study, balancing the utility of the information with the costs of conducting the study. Finally, all the elements above will be considered and a protocol for testing the effect of universal screening using ultrasound drafted.

9. Target population:

The current application is in response to a commissioned call, hence the target population was determined in the brief. The target population will be all pregnant women in the UK, who are currently offered two routine ultrasound scans. The primary aims of the first (at 11-14 weeks of gestation) are to confirm viability; establish accurate gestational age from the measurement of fetal CRL; identify multiple pregnancies (and in these determine chorionicity); and measure fetal NT thickness, as part of the “Combined Screening test” for Trisomies 21,18 and 13. The second scan, at 18-21 weeks, aims mainly to detect congenital abnormalities and specifically for the detection of anencephaly ; open spina bifida; cleft lip; diaphragmatic hernia; gastroschisis; exomphalos; serious cardiac anomalies; bilateral renal agenesis; lethal skeletal dysplasia and chromosomal anomalies (mainly Trisomy 18 and 13)(5, 6).

The choice of offering the scan to all women is in keeping with national screening policy and the fact that, although women at high risk of fetal abnormality have an increased chance of fetal anomalies, overall the majority of fetal anomalies occur in low-risk women (62, 63). The timing of screening, i.e. in early pregnancy, is purposeful, and is informed in part by thinking about the likely nature of earlier pregnancy termination, which may mitigate the risks of an adverse outcome (10, 11, 16, 17, 64).

It is also likely to be associated with higher satisfaction rates. Studies on the impact of prenatal congenital fetal anomaly diagnosis for parents suggest significant emotional and psychological distress, depression and anxiety after disclosure of results at both 6 week and 6 month follow-up (56). In addition, high levels of psychological distress are seen in women following pregnancy termination for fetal anomaly (65), but there are much greater levels of post-traumatic stress symptoms in women undergoing second trimester compared to first trimester termination (OR 9.3) at 6 weeks post procedure (10). In a longitudinal study with follow-up of up to 7 years (11) advanced gestational age at pregnancy termination was associated with higher levels of grief; in contrast, post-traumatic stress and long-term psychological morbidity were rare in women undergoing termination prior to 14 weeks of gestation.

Nevertheless, the advantages of earlier diagnosis need to be balanced against lower sensitivity (in particular cardiac defects and spina bifida); false positive rates; and cost. The first can be overcome by maintaining the second scan; the second and third have been under-studied in the existing literature.

The focus of the analysis – all (unselected) pregnant women in early pregnancy – is informed by evidence, screening policy a potential beneficial net effect of earlier screening.

10. Inclusion/Exclusion Criteria:

All pregnant women will be eligible. The hypothetical care pathway to be evaluated is one where all pregnant women are still offered two routine scans, but where anomaly detection would not be assessed only at the second scan, but also at the first. We will define care pathways for women who do and those who do not wish to take up such screening.

No primary research will be undertaken; however, we will evaluate the potential contribution first trimester ultrasound might be able to play in the early detection of structural defects, based on what is known in studies; create a protocol-driven methodology for performing this scan, and conduct an economic analysis and a value of information study as described.

11. Setting/context:

The setting for the study is prenatal care of populations of mixed risk, which is shared between primary and secondary care. Data collection and analysis are discussed in the respective sections above.

For search the strategy of data synthesis please see WP 1 in section **7. Research Plan**.

The context of the Health Economic Analysis merits specific mention. Putting all ethical aspects aside, health economists most frequently measure the health impact of a disease or intervention using Quality-Adjusted Life Years (QALYs); in fact this is a requirement for all technology assessment submissions made to the National Institute for Health and Care Excellence in England. The basic premise behind the QALY is that when assessing the impact of a disease or intervention, the effect upon quality of life as well as quantity of life is considered. Quality of life is usually measured on a scale anchored at 0 and 1 - where a value of 1 signifies perfect health and a value of 0 signifies death/non-existence. These scores are then used to weight the number of life years lived. Assuming then, that severe health complications might carry a quality of life value of e.g. 0.5, then a child living with these complications for 20 years would accrue 10 QALYs ($0.5 * 20$). This is clearly inferior to a life in perfect health (20 QALYs): living with the complications would mean a loss of 10 QALYs compared to perfect health.

The question we must ask ourselves in the context of this study is how we can assess this in relation to terminated pregnancies. In that case, the comparison would be a terminated pregnancy with associated 0 QALYs versus a child with complications over 20 years with associated 10 QALYs. Therefore, from a QALY perspective, termination of pregnancy would always result in a loss of QALYs when compared with a child with complications (unless living with complications resulted in negative QALYs over the 20 year span) even though this may have been at the wish of the mother or parents. How this translates into whether a detailed anomaly scan at first trimester has the potential to be cost-effective is something the project team and PPV group have thought about deeply.

Although the standard 'cost per QALY' methodology is the most frequently used approach to economic evaluation because it provides a common measure of outcomes and facilitates cross-intervention comparisons, in this instance it may not be appropriate for the reasons described above and in Section 7. In view of the fact that different parties stand to be affected by this policy, if it is adopted, we have proposed the use of a cost-consequence analysis, which by allowing a range of various outcomes to be considered (perhaps including the QALY), may be one way to answer such a controversial question and would allow policy makers to contextualise the results. The detailed description in WP 4 of section **7. Research plan** deals in more detail with the issues.

12. Sampling

A detailed description of this is given in the Research Plan section. Briefly, sampling of the literature will be undertaken using systematic review methodology to ensure that as far as possible all relevant publications are reviewed. In terms of sampling of participants for the consensus procedure, we have formed a very broad

13. Data collection:

A detailed description of sampling is given in section 7 (Research Plan). Briefly, data will be collected from systematic reviews and will result in candidate papers; a database will be created in EndNote (Thomson Reuters). Data from individual studies will be extracted and authors contacted where this is not possible from published results. For scoping opinions web-based tools (REDCap) will be used to gather the views of a range of professional stakeholders on the elements of the screening test, design of a screening trial, and the feasibility of population screening. The applicants include healthcare professionals from all areas of prenatal care. They are strategically positioned in, and have strong links with, relevant organisations, and this will ensure the feasibility of wide ranging sampling for scoping and consensus building (Antenatal Results and Choices (ARC); Tiny Tickers; Spina Bifida - Hydrocephalus - Information - Networking – Equality (SHINE); National Childbirth Trust; Royal College of Midwives; Royal College of Obstetricians and Gynaecologists; Society & College of Radiographers; National Screening Committee; British Medical Ultrasound Society; British

Maternal Fetal Medicine Society; International Society of Ultrasound in Obstetrics and Gynecology; Fetal Medicine Foundation, amongst others).

14. Data analysis:

A detailed description of this is given in 7. Research Plan. Extracted data from systematic reviews will be analysed using RevMan (66) software or STATA for more complex analysis such as metaregression, or where better random-effects estimators are required(67).

15. Dissemination and projected outputs:

Our dissemination plan reflects the ultimate purposes of this study, i.e. derive a protocol for the first trimester scan and estimate the value of continued research in the area, rather than inform policy directly. However, should our results suggest that no further research is worthwhile, the economic model will be used to inform policy and we will adjust our dissemination strategy accordingly.

